intramuscularly, micronized progesterone orally, micronized progesterone capsules administered vaginally, compounded micronized progesterone vaginal suppositories, progesterone vaginal gel, and progesterone vaginal suppositories. The authors defined successful treatment as viability post 20 weeks' gestation. They excluded 207 women from analysis, including those who received treatment >72 hours post-mifepristone or in whom misoprostol had been used (n=38), were lost to follow-up at <20 weeks' gestation (n=112), or who opted to complete the abortion (changed mind again, n=57). Of 547 women in the analysis, treatment was successful in 261 (48%) women including 257 births and 4 women LTFU after 20 weeks. Subgroups with the highest success rates included 31 women treated with high-dose oral progesterone 400 mg twice daily for 3 days followed by 400 mg daily until end of "first trimester" (68%) and 125 women who received progesterone in oil IM initially or exclusively (64%). Notably, efficacy was higher with more advanced gestational age. The authors estimated that 25% of women would have continued the pregnancy even without treatment; that statistic implies no

PROTOCOL TITLE: A Randomized Trial of Mifepristone Antagonization with High-Dose Progesterone to Prevent Medical Abortion

treatment effect for woman earlier than 6 weeks gestation and an overall effect size of any treatment to be 23%.

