- If the pregnancy is expelled, the visit will be considered an exit visit.
 - Collect remaining study drug and diary.
 - Refer subject to the original referral location (PPMM Sacramento B Street Clinic, FPA Sacramento Clinic or the UCD Family Planning clinic) for completion of follow-up care; a patient from PPMM or FPA can request to complete care at UCD.
 - Referrals for PPMM-referred subjects returning to PPMM will be made to the Sacramento B Street Clinic.
 - Referrals for FPA-referred subjects returning to FPA will be made to the Sacramento Clinic.
 - The subject will be exited from the study after a final outcome is determined by the clinical team.
- If the subject is continuing in the study, she will be reminded of the correct timing of study treatment intake, to fill our her diary daily, and to bring her diary and study drug with her to the next visit.
- Study exit visit: schedule for study day 15-17
 - Scheduled exit visits (study day 15-17) should occur through the original referral source (PPMM, FPA or the UCD Family Planning clinic) but a patient from PPMM or FPA can request to complete care at UCD.
 - Visits for PPMM-referred subjects returning to PPMM will occur at the Sacramento B Street Clinic.
 - Visits for FPA-referred subjects returning to FPA will occur at the FPA Sacramento Clinic.
 - Diary will be reviewed and collected from the participant.
 - Study drug container will be collected and remaining drug counted by study staff.
 - Two 5 mL tubes of blood will be obtained for serum hCG and progesterone level.
 - Ultrasonography will be performed to evaluate for presence of the gestational sac, interval growth and presence of gestational cardiac activity; the exam should preferentially be performed vaginally unless the gestational age or subject anatomy requires abdominal sonography for clearer visualization.
 - A surgical abortion will be performed through routine care if pregnancy has not passed and patient desires.
- If a subject desires to exit the study early (have a surgical abortion prior to Day 15-17), the exit visit procedures should be performed on the day of the surgical abortion.

PROTOCOL TITLE: A Randomized Trial of Mifepristone Antagonization with High-Dose Progesterone to Prevent Medical Abortion

- Unscheduled visits: to occur if the subject has any medical concerns or experiences heavy bleeding which may indicate loss of viability or passage of pregnancy
 - Diary will be reviewed.

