8) Data and/or Specimen Management and Confidentiality

Sample size:

- Delgado and colleagues estimate the oral progesterone regimen in this study has an efficacy of 68% (10) and that about 25% of women will expel the pregnancy after mifepristone 200 mg treatment alone, (10,12) implying an effect size of ~43%.
 - Sample size needed for Effect1=68%, Effect2=25%, Alpha=0.05, Beta=0.20: 20 per group.
 - Sample size needed for Effect1=70%, Effect2=25%, Alpha=0.05, Beta=0.20: 18 per group.
- We plan a convenience sample of 40 women (approximately 20 per group) which is enough to answer the primary question of efficacy proposed by Delgado and colleagues.
 - Should no obvious benefit be observed then a larger trial would not be indicated.
 - If some benefit is present, then a sample size could be estimated for a larger trial with considerations of sample size estimates for different gestational age ranges.
 - Importantly, if we cannot feasibly recruit from this population, then a larger study would also need to consider alternative mechanisms for enrollment.
- Recruitment: expect 36 subjects from PPMM and FPA (competitive enrollment) and 4 subjects from UCD.

Data Analysis Plan:

We will include all women randomized and perform intent-to-treat analysis with no apparent exclusions. In addition, a second analysis will be conducted with a per-protocol population, excluding women who do not report ingesting the study medication per protocol. Evaluations will include primary outcome (continuing pregnancy), expulsion rates, adverse effects, and treatment continuation rates.

At time of enrollment, we will collect baseline demographic data, including age, race, ethnicity, education level, and medical history (including obstetric and gynecologic history).

PROTOCOL TITLE: A Randomized Trial of Mifepristone Antagonization with High-Dose Progesterone to Prevent Medical Abortion

Fisher's Exact Testing will be used to compare outcomes and baseline characteristics in the two groups.

While not powered to detect a statistically significant difference among the two groups for secondary outcomes, exploratory analyses will be performed to identify possible trends and areas of interest for a subsequent larger trial. Chi square and Fisher's Exact Tests will be utilized to compare dichotomous variables as appropriate.

Data Management Plan:

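### Section 8 enrols exactly the 20 per group it calculates for 68% v 25%, with no allowance for early exit, so the stated 80% power needs every two-week outcome observed and is not reached under Fisher's exact test even then

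*Combined protocol and SAP*

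**What the plan says.** Section 8 (Sample size) gives two calculations: "Sample size needed for Effect1=68%, Effect2=25%, Alpha=0.05, Beta=0.20: 20 per group" and "Sample size needed for Effect1=70%, Effect2=25%, Alpha=0.05, Beta=0.20: 18 per group". It then sets enrolment and claims sufficiency: "We plan a convenience sample of 40 women (approximately 20 per group) which is enough to answer the primary question of efficacy proposed by" the case-series authors. The same list adds that, if no obvious benefit appears, a larger trial would not be indicated.

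Section 8 (Data Analysis Plan) defines the main analysis: "We will include all women randomized and perform intent-to-treat analysis with no apparent exclusions". It names Fisher's exact test for comparing outcomes. Section 6 makes the primary endpoint a pregnancy with cardiac activity after two weeks of study treatment.

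Section 7 (Study exit visit) provides for women who leave before that time: "If a subject desires to exit the study early (have a surgical abortion prior to Day 15-17), the exit visit procedures should be performed". Those procedures take place the same day as the early abortion. Section 11 lets participants discontinue for any reason. No section gives an expected exit rate, a replacement rule, or a rule for classifying a woman who leaves early with cardiac activity present.

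Section 3 describes the series behind the 68%. It reports that figure for 31 women on the oral regimen, after the series had removed women who "were lost to follow-up at <20 weeks' gestation (n=112), or who opted to complete the abortion (changed mind again, n=57"). Success there meant viability beyond 20 weeks' gestation.

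**The concern.** The number calculated and the number enrolled are the same. The calculation treats each of the 40 women as supplying a two-week outcome. All of them are seeking surgical abortion, and the protocol describes how one may have it before day 15-17. An ultrasound on the day of an early elective abortion shows status on that day, not at two weeks.

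The assumed 68% was computed after women who left or were lost had been taken out. It is applied to an analysis that keeps them in.

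The stake is how a null result will be read. Section 8 plans to treat absence of obvious benefit as a reason not to run a larger trial. That inference leans on a 20% risk of missing a true 68% v 25% difference, and the enrolment and analysis as written give a larger risk.

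**Working it through.** **Inputs.** Rates 68% and 25%, alpha 0.05, Beta 0.20, 20 per group, all randomized analysed, Fisher's exact test (all Section 8). Sidedness is not stated; I take it as two-sided because that reproduces the plan's numbers. I read 25% as continuation without treatment, following Section 3: "The authors estimated that 25% of women would have continued the pregnancy even without treatment". Section 8 words it as expulsion; the two should be reconciled, and the calculation works only with continuation.

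**Reproducing the plan.** The arcsine formula is

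h = 2·asin√p1 − 2·asin√p2, n per group = 2(1.960 + 0.842)²/h², power = Φ(h√(n/2) − 1.960).

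- 68% v 25%: h = 1.9391 − 1.0472 = 0.8919, n = 19.7, so 20. This matches.
- 70% v 25%: h = 0.9351, n = 17.95, so 18. This matches.
- Power at 20 per group, 68% v 25%: Φ(0.8919 × 3.1623 − 1.960) = Φ(0.860) = 80.5%.

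The pooled-variance formula without continuity correction gives 20 and 19, and 80.2% power at 20 per group.

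**The planned test, no exits.** Enumerating both binomials, two-sided Fisher's exact test has 68.5% power at 20 per group. It needs 24 per group for 80%.

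**Adding exits.** Let d be the share of each arm that exits electively or is lost. The values of d are assumptions. Expulsion or loss of cardiac activity is an observed outcome and is not part of d. If exits count as not continuing, the rates become 0.68(1−d) and 0.25(1−d). If they count as continuing, d is added to each.

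| d | Rates, exits not continuing | Sizing formula | Fisher | Sizing formula, exits continuing | Fisher, exits continuing |
|---|---|---|---|---|---|
| 0% | 68.0% v 25.0% | 80.5% | 68.5% | 80.5% | 68.5% |
| 5% | 64.6% v 23.8% | 76.6% | 64.1% | 75.9% | 62.2% |
| 10% | 61.2% v 22.5% | 72.4% | 60.0% | 71.1% | 56.6% |
| 20% | 54.4% v 20.0% | 63.8% | 51.7% | 61.4% | 47.4% |

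If exits are instead left out, the sizing formula gives 76.3% with 18 per group and 71.3% with 16. Fisher's exact test gives 70.1% with 19, 68.4% with 18 and 57.2% with 16. It does not fall smoothly because the test is discrete, but it stays well below 80% throughout.

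**The case against.** **The choice of test costs more than modest exit.** Moving from the sizing formula to Fisher's exact test takes 12 points (80.5% to 68.5%); 5% exit takes about 4. This stands. A reader might infer that Beta=0.20 would be met if nobody left early. Under the planned test it would not.

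**There is some reserve under the second sizing line.** At 70% v 25%, 20 per group gives 84.1%, and 80.3% after 5% exit counted as not continuing. That is true, but the plan does not present this line as a dropout allowance, and its main line has none.

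**The 68% could be too low.** A reader might infer that it is inflated because exits were removed. The documents do not establish that. The series counted viability after 20 weeks, so losses between two and 20 weeks count against its 68% but would not count here. If the two-week rate were 74% (an assumption), the sizing formula would still give 82.9% after 10% exit. Nor does Section 3 say how many removed women were on the oral regimen.

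**No exit rate carries over from the series.** Its change-of-mind share is 57/(754 − 38) = 57/716 = 8.0%. Those women had sought reversal and were followed far longer than two weeks. The figure should not be taken as an expected rate here.

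**The loss depends on coding and on exits in both arms.** The documents state no coding. Exit in placebo only, counted as not continuing, would raise nominal power (83.0% at 5%), though it would bias the comparison. With exits in both arms, the sizing formula loses power under all three codings.

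**This is a convenience sample and a first step.** So it is described, but the same sentence claims sufficiency, and a decision about a larger trial hangs on it.

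**Conclusion.** The point holds as a statement about the power claim. Section 8 leaves no margin: 80.5% by its apparent formula requires all 40 two-week outcomes, and Fisher's exact test gives 68.5% even with all of them. With exits in both arms counted as not continuing, 5% to 20% exit brings power to about 77% to 64% by the sizing formula and 64% to 52% by Fisher's exact test. At 10%, a true 68% v 25% difference would be missed about 28% of the time by the formula and 40% by the planned test, against the stated 20%.

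These figures rest on assumed exit rates, equal exit in the two arms, a stated coding of exits, two-sided testing, and 25% read as continuation. A small number of exits matters little: one woman left out (19 v 20) gives 79.5% by the formula. The documents do not support saying that 68% is too high, or that any particular share of women will leave.

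**What to change.** Keep N=40. In Section 8, replace the claim that the sample is sufficient with text such as:

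> With 20 per group and every two-week outcome observed, power for 68% v 25% is about 80% by the sizing formula and 68% by two-sided Fisher's exact test. If 5%, 10% or 20% of women in each arm (assumed) exit electively or are lost and are counted as not continuing, power is about 77%, 72% or 64% by the sizing formula (64%, 60% or 52% by Fisher's exact test).

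State in the Data Analysis Plan how a woman who exits electively or is lost before two weeks is counted in the intent-to-treat analysis, so that the imputation behind these figures is explicit. Temper the statement that no obvious benefit means a larger trial is not indicated, so that it reflects this power.

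The cost is a few sentences and a less favourable stated power. No patients or procedures are added.

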The dilemma that has been created around medical abortion reversal only exists because of the void in high-quality research addressing the issue; basic concepts need to be addressed to begin to understand if medical abortion reversal is actually possible. These case series reports (8,11,12) lack control groups, and the reports by Delgado and colleagues (8,12) involved experimental treatment without consent or oversight. Unfortunately, even without such trials, conservative lawmakers are using these case reports as medical gospel and passing laws stipulating reversal as fact. In 2015, Arkansas implemented mandatory abortion reversal counseling followed by Arizona (later repealed in 2016), South Dakota, and Utah. The Idaho governor signed such a counseling law on March 20, 2018, which went into effect on July 1, 2018. Numerous other states have initiated bills to create similar laws that have not passed. Conversely, Louisiana Department of Health report in April 2017 found “neither sufficient evidence nor a scientific basis to conclude that the effects of an abortion induced with drugs or chemicals can be reversed” (13). In 2015 and reiterated in August 2017, the American Congress of Obstetrics and Gynecology publicly stood against laws mandating reversal information as lacking scientific standing (14).

In this study, we propose a double-blind randomized trial to evaluate the potential impact of progesterone treatment on early pregnancies exposed to mifepristone. This study is also a first step to understanding if large studies evaluating mifepristone antagonization with high-dose progesterone are indicated and if placebo-controlled randomized trials can be successfully completed when evaluating this question.

4) Inclusion and Exclusion Criteria

Inclusion Criteria

1. Pregnant females 18 years and older at enrollment.
2. Seeking surgical abortion at 44-63 days gestation on Study day 1.
3. Have received counseling and signed informed consent per UCD standard procedures for surgical abortion.
4. Singleton pregnancy
5. Presence of embryonic gestational cardiac activity on transvaginal ultrasonography.
6. English-speaking
7. Willing to sign informed consent and follow study protocol.
8. Willing to experience potential expulsion of the pregnancy with mifepristone treatment.

Exclusion Criteria

1. Medical contraindications to medical abortion.
 - a. Poorly controlled hypertension (systolic BP >160 or diastolic BP >95)

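### With 20 women per group, a result without benefit can refute the claimed 43-point effect but cannot by itself show that no larger trial is warranted, and no confidence interval is planned to mark the difference

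*Combined protocol and SAP*

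**What the plan says.** Section 8, Sample size, gives 20 per group for 68% versus 25% (alpha 0.05, beta 0.20) and 18 per group for 70% versus 25%. It plans 40 women, "which is enough to answer the primary question of efficacy proposed by" the authors of the cited case series. Two bullets beneath that sentence say what follows from the result. One is "Should no obvious benefit be observed then a larger trial would not be indicated". The other is "If some benefit is present, then a sample size could be estimated for a larger trial". Neither says how large an observed difference counts as benefit.

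Section 8, Data Analysis Plan, specifies an intent-to-treat analysis of all randomized women and a per-protocol analysis. Fisher's "Exact Testing will be used to compare outcomes and baseline characteristics in the two groups". No effect estimate or confidence interval is named; the only intervals in the document are in the Section 3 tables of earlier studies.

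Section 3 (Background) calls the trial a "first step to understanding if large studies evaluating mifepristone antagonization with high-dose progesterone are indicated". In Section 2, research questions 2 and 3 are both conditional on progesterone possibly being of benefit, and question 3 then asks what sample size a validating trial would need.

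On the control rate, Section 3 reports: "The authors estimated that 25% of women would have continued the pregnancy even without treatment". Section 8 describes the same 25% as women who expel the pregnancy after mifepristone alone.

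**The concern.** The sample size rationale is narrow: 40 women are enough to test a very large claimed effect. The no-benefit bullet is wider, because it moves from that test to whether any larger trial is needed. Between the two lie moderate effects that 20 per group cannot exclude. A non-significant Fisher p-value does not show which of them remain possible.

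Whether large studies are indicated is a stated purpose of the trial, so this bullet bears on one of its main conclusions. If it is followed as written, a null result could close a question on which the data are silent.

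**Working it through.** **1. The plan's own figure.** Inputs from Section 8: p1 = 0.68, p0 = 0.25, mean 0.465, two-sided alpha 0.05 (sidedness is not stated), power 80%.

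n = [1.96·√(2·0.465·0.535) + 0.842·√(0.68·0.32 + 0.25·0.75)]² / 0.43² = 19.9, so 20 per group, as stated. The arcsine formula gives 19.7 and, for 70% versus 25%, 17.95, which match the stated 20 and 18. The calculation treats 25% as the continuing rate, and the steps below do the same.

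**2. What a result leaves open.** Newcombe 95% interval for d = p1 − p0, with (l, u) the Wilson limits in each arm: upper limit = d + √[(u1 − p1)² + (p0 − l0)²], and lower limit = d − √[(p1 − l1)² + (u0 − p0)²]. For 5/20 the Wilson limits are 0.112 and 0.469. Equal rates of 5/20 therefore give 0 ± √(0.219² + 0.138²) = ±0.259.

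| Progesterone v placebo | Difference (points) | 95% interval (points) | Below 43? |
|---|---|---|---|
| 5/20 v 5/20 | 0 | -25.9 to +25.9 | yes |
| 8/20 v 5/20 | +15 | -13.4 to +40.4 | yes |
| 9/20 v 5/20 | +20 | -9.1 to +45.0 | no |

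Equal rates exclude 43 points but not the 23-point overall effect (48% less 25%) that Section 3 itself derives.

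**3. Chance of a wrong no-go.** Exact binomial enumeration, 20 per arm, 25% continuing on placebo. Two lenient readings of no obvious benefit: no observed advantage, or an advantage of 10 points or less (2 women in 20).

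| True rates | No advantage | 10 points or less |
|---|---|---|
| 48% v 25% | 8.4% | 23.7% |
| 51.5% v 25% | 5.4% | 17.1% |
| 68% v 25% | 0.3% | 1.9% |

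The 48% is the whole case series (261/547). The 51.5% pools its 6- to 8-week rows, (52 + 50 + 54)/(113 + 102 + 88) = 156/303, which lie closer to the 44-63 days enrolled. Both are illustrative. The series is uncontrolled and mixes routes, and its endpoint differs from cardiac activity at two weeks: "The authors defined successful treatment as viability post 20 weeks".

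**4. Dependence on the placebo rate.** A 43-point gain is possible only if the placebo rate is at most 100 − 43 = 57%. Suppose, as an assumption, that 70% continued on placebo. The largest possible gain is then 30 points. A result of 17/20 v 14/20 has an interval of -11.1 to +39.0. It would be said to exclude 43 points although progesterone is 15 points ahead and 43 was never attainable.

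**5. What the trial can still show.** With no true effect, the upper limit falls below 43 points in 90.5% of trials at 25% continuing in both arms, and in 87.1% at 40%.

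**The case against.** The bullet is planning rationale, placed under a sentence that confines the trial to one published claim. It can be read as saying only that, if the claimed effect does not appear, that claim does not justify a larger trial. Section 3 calls the study a first step, and nothing says how a null result will be reported. No smallest worthwhile effect is named, so moderate effects matter only if someone would mount a trial for them. The 23-point figure pools all regimens, whereas the oral regimen used here is credited with 68%. How pragmatic a no-go should be is partly the investigators' choice.

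Most of this stands, and it limits the point. A reader might infer that no obvious benefit means a non-significant Fisher test, which would make a wrong no-go 77% likely at 48% versus 25% (70% at 51.5% versus 25%). The documents do not support that reading: the companion bullet asks only for some benefit, and research questions 2 and 3 only for possible benefit. A reader might also infer that 40 women are too few for the stated aim, or that a null result will be published as settling the matter. The first is not claimed here, since the sizing reproduces. The second is prediction.

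What the objection does not remove is the width of the interval. It needs no figure from the case series, and it holds even when no advantage at all is observed.

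**Conclusion.** The point holds in a limited form. The sample is defensible for testing the 43-point claim. The no-benefit bullet goes further than 20 per group allows, and the plan has no interval to show where the evidence stops. On the lenient reading the documents favour, the risk of a wrong no-go is modest: about 8% to 24% at the illustrative 48% versus 25%, and 0.3% to 2% at the claimed effect. Those figures assume 25% continuing on placebo and 20 evaluable women per arm.

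Refuting the 43-point claim also depends on the placebo rate, which the documents word inconsistently. Expulsion is not the complement of continuing pregnancy, so the Section 8 wording cannot simply be inverted; the two statements must be reconciled. This should be changed, although it does not invalidate the primary test.

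**What to change.** 1. In the Data Analysis Plan, pre-specify a 95% confidence interval (for example Newcombe) for the intent-to-treat risk difference in continuing pregnancy, reported with both arms' observed rates. State that Fisher's test governs significance and that the interval serves only to say which effects are excluded. The two can disagree: 12/20 v 5/20 gives Fisher p = 0.054 with an interval of +4.4 to +57.8 points, and would be reported as not significant.
2. Reword the no-benefit bullet: a result without benefit excludes only effects above the upper limit and is otherwise inconclusive for smaller effects.
3. State that the 43-point claim is refuted only if the upper limit is below 43 points and the observed placebo continuing rate is low enough for a 43-point effect to be possible (at most 57%). Reconcile the two descriptions of the 25%.
4. Optional: a smallest effect of interest, set in advance by the investigators, below which they would conclude that no larger trial is needed.

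The cost is a few sentences and one interval, with no change to sample size, endpoint, primary test or visits. The downside is that the trial can claim less after a null result. With no true effect at 25% to 40% continuing, it still excludes 43 points in about 87% to 91% of trials. It gives up the broad no-go that the present wording allows in 56% to 57% of such trials (no observed advantage) or 79% to 82% (10 points or less). With a margin of 23 points, purely for illustration, a firm no-go would follow in only 35% to 42% of them. That trade-off is why the margin is left to the investigators.

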A Randomized Trial of Mifepristone Antagonization with High-Dose Progesterone to Prevent Medical Abortion

NCT03774745

Protocol and SAP date: July 18, 2019 (version 10)

PROTOCOL TITLE: A Randomized Trial of Mifepristone Antagonization with High-Dose Progesterone to Prevent Medical Abortion

1) Protocol Title

Title: A Randomized Trial of Mifepristone Antagonization with High-Dose Progesterone to Prevent Medical Abortion

2) Objectives

Research questions:

1. Does high dose oral progesterone treatment increase the continuing pregnancy rate in women 44-63 days gestation exposed to mifepristone without misoprostol treatment?
2. If oral progesterone may be of benefit, do some characteristics of the pregnancy (e.g., gestational age) or patient (e.g. parity) potentially impact the outcome?
3. If oral progesterone may be of benefit, what sample size would be needed to validate such an outcome for various gestational age ranges in a prospective placebo-controlled randomized trial?
4. How long does it take to recruit women seeking surgical abortion to participate in a double-blind randomized trial evaluating oral progesterone for antagonization of mifepristone treatment for abortion?

Hypothesis: High-dose oral progesterone initiated 18-24 hours after mifepristone 200 mg in early pregnancy will result in more continuing pregnancies after 2 weeks of treatment than placebo.

3) Background

Medical abortion commonly refers to early pregnancy termination (usually before 10 weeks' gestation) performed without primary surgical intervention and resulting from the use of abortion-inducing medications (1). The use of medications to cause abortion has been around for almost 70 years but the modern era of medical abortion treatment evolved with the development of mifepristone (1), a progesterone-receptor blocker with an affinity for the receptor greater than progesterone itself (2).

Early research into modern medical abortion regimens took a leap forward with the discovery that adding a prostaglandin analogue within a few days after mifepristone significantly improved the efficacy of the treatment (3). In the late 1980s, France, China, Switzerland and the UK became the first countries to make medical abortion treatment clinically available, with regimens using mifepristone 600 mg followed 36-48 hours later by a prostaglandin analogue, restricted to use up to 49 days gestation.

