Zheng 1989 [15]	600 mg (single dose)	204	42 days	7 days	65%	31% (25–38%)
Zheng 1989 [15]	600 mg (single dose)	95	49 days	7 days	53%	46% (37–56%)

NS, not specified.

^a One additional participant was later found to have an ectopic and is excluded from the total here.

^b Three additional participants had a missed abortion at time of treatment and are excluded from the total here.

13 studies meeting appropriate criteria to be included in the review with continuing

PROTOCOL TITLE: A Randomized Trial of Mifepristone Antagonization with High-Dose Progesterone to Prevent Medical Abortion

pregnancy rates ranging from 8% to 46% when patients were assessed generally 1-2 weeks after mifepristone ingestion. Of note, the studies with the lowest rates of continuing pregnancies typically included women earlier in gestation.

Another review was published in 2017 by Davenport, Delgado and colleagues (10) openly as a rebuttal to the review from Grossman et al (9). This review, published in a journal not indexed in Pubmed, included only three of the same papers meeting inclusion criteria for the analysis by Grossman et al and excluded four of the papers included by Grossman et al stating that these studies did not always use ultrasound to designate if a viable pregnancy was present. These authors report a mean percentage of continuing pregnancies of only 12.6%, with most studies using mifepristone 600 mg or more. Recently, two additional case series have been published. The first is an Australian description of 3 women (at 43 days, approximately 53 days, and 61 days gestation) who initiated treatment with progesterone vaginally for 14 days at 28, 3.5, and 31 hours, respectively, after ingesting mifepristone (11). The first two women had continuing pregnancies and delivered healthy newborns, and the third women experienced a miscarriage on the day she initiated progesterone treatment.

The second is a report from [name] abortionreversalpill.com network (12). Published again in the same journal not indexed in Pubmed, this case series includes 754 women treated in

various ways by 325 different providers with "high-dose" progesterone, including progesterone in oil

Gesta-tional Age	Total	Reversal	Reversal Failure	Reversal %	P value	95% Confidence Intervals
5 weeks	76	19	57	25%	0.5	0.15-0.35
6 weeks	113	52	61	46%	<0.001	0.37-0.55
7 weeks	102	50	52	49%	<0.001	0.39-0.59
8 weeks	88	54	34	61%	<0.001	0.51-0.72
9 weeks	30	23	7	77%	<0.001	0.62-0.92

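### Fisher's exact test is valid but gives about 69-72% power, not 80%, and no suitable method is named for the continuous hCG and progesterone endpoint

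*Combined protocol and SAP*

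**What the plan says.** Section 8, Sample size, plans about 20 women per group from 68% v 25%, Alpha=0.05 and Beta=0.20, and gives 18 per group for 70% v 25%. It does not state the sidedness.

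Section 8, Data Analysis Plan, applies one method to everything: Fisher's "Exact Testing will be used to compare outcomes and baseline characteristics in the two groups". For secondary outcomes it adds that "exploratory analyses will be performed to identify possible trends and areas of interest for a subsequent larger trial", and that chi-square and Fisher's Exact "Tests will be utilized to compare dichotomous variables as appropriate". The outcomes to be analysed are listed thus: "Evaluations will include primary outcome (continuing pregnancy), expulsion rates, adverse effects, and treatment continuation rates". Hormone levels are not in that list, although Section 6 makes their change over treatment a secondary endpoint and Section 7 schedules blood draws at enrollment, days 4 and 8, and exit.

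On gestational age, Section 2 asks "do some characteristics of the pregnancy (e.g., gestational age) or patient (e.g. parity) potentially impact the outcome" and "what sample size would be needed to validate such an outcome for various gestational age ranges in a prospective placebo-controlled randomized trial", both only if progesterone may be of benefit. Section 8 answers with one conditional remark, that "a sample size could be estimated for a larger trial with considerations of sample size estimates for different gestational age ranges". It names no ranges.

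**The concern.** The sample size rests on a large-sample formula, but the data are to be analysed with a test whose true type I error at this size is well under the nominal 5%. The unused error is lost power. In a trial of 40 women, whose negative result is meant to argue against a larger trial (Section 8, Sample size), moving from a planned 80% to about 70% raises the risk of missing the assumed effect from 20% to about 30%.

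Fisher and chi-square compare categories. Applied to a hormone change they require cut-points, and none are given. Leaving the method open invites a choice after unblinding and discards information already collected. The later samples also come from a selected group: a woman exits once cardiac activity is absent or the pregnancy is expelled (Section 7), so those still giving blood at day 8 and day 15-17 are mainly those whose pregnancies continued.

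**Working it through.** **Inputs.** Continuing-pregnancy rates 68% v 25%, alpha 0.05, power 0.80, 20 per group (Section 8, Sample size). Two-sided testing is assumed. I read 25% as the rate continuing on mifepristone alone, as in Section 3; the Sample size text says 25% will expel, and the calculation works only on the first reading.

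**1. The plan's own figure.** Pooled-variance formula without continuity correction, mean rate 0.465:

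n = [1.96·√(2·0.465·0.535) + 0.8416·√(0.68·0.32 + 0.25·0.75)]² / 0.43² = (1.3825 + 0.5357)² / 0.1849 = 19.9, so 20 per group. For 70% v 25% it gives 19; the arcsine formula gives 20 and 18. The stated sizes therefore reproduce, but neither formula describes Fisher's test.

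**2. Exact size and power.** For arms n1 and n2, power = Σ Bin(a; n1, 0.68)·Bin(b; n2, 0.25) over all tables (a, b) that the test rejects. Size uses the same sum with a common rate. Boschloo's test orders tables by the Fisher p-value and takes the largest cut-off whose size, maximised over the common rate, stays at or below 0.05. At 20/20 that cut-off is a Fisher p of 0.0915.

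| Progesterone/placebo | Fisher size at 25% | Fisher power | Boschloo maximum size | Boschloo power | Gain (points) |
|---|---|---|---|---|---|
| 20/20 | 0.024 | 0.685 | 0.046 | 0.776 | 9.1 |
| 21/19 | 0.034 | 0.718 | 0.048 | 0.802 | 8.5 |
| 19/21 | 0.034 | 0.703 | 0.048 | 0.789 | 8.6 |
| 22/18 | 0.030 | 0.721 | 0.045 | 0.781 | 6.0 |
| 18/22 | 0.030 | 0.713 | 0.045 | 0.792 | 7.9 |

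The nearby splits matter because the plan says approximately 20 per group and describes no blocking. At 70% v 25% and 20/20, Fisher gives 0.731 and Boschloo 0.816. Fisher first reaches 80% for 68% v 25% at 24 per group (0.819).

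An example at 20/20: 12 v 5 continuing pregnancies gives a Fisher p of 0.0536. Fisher does not reject; Boschloo does, because 0.0536 is below 0.0915.

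**3. Hormone endpoint.** Take log values with equal variance σ² at baseline and follow-up and correlation ρ.
- Change score: variance 2σ²(1 − ρ).
- Baseline-adjusted: variance σ²(1 − ρ²).
- Ratio: (1 − ρ²) / [2(1 − ρ)] = (1 + ρ)/2, which is 75%, 85% or 95% at ρ = 0.5, 0.7 or 0.9.

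The documents give no ρ, so these values are assumed. If the value were instead split at its median so that Fisher or chi-square could be used, a normal outcome would keep 2/π = 64% of the information, or about 25 of 40 women (40 × 0.637).

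**4. Precision by gestational age.** If about 12 women per arm were early and 8 late (enrolment uniform over 44-63 days, assumed), 7/12 has an exact 95% CI of 27.7-84.8% and 5/8 of 24.5-91.5%. Such rates can be described but hardly tested.

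**The case against.** A valid test needs no correction. Fisher protects type I error, it is named in advance, and randomization supports it. Power below 80% is a sample-size matter, and changing the primary test while women may already be enrolled has a cost in credibility. Section 8 also calls its 40 women a convenience sample and its secondary work exploratory and unpowered. The hormone endpoint is defined as a change, so baseline is already used.

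Much of this stands. Fisher may stay primary if its power is restated. Against a change score the saving from baseline adjustment is modest, 5% of variance at ρ = 0.9. What the objection does not answer is that the plan implies 80% power for a test that gives about 70%, and that it names no method suited to a continuous endpoint.

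A reader might go further and infer that the primary test should be stratified by gestational age, because question 3 depends on it and Section 3 notes that "the studies with the lowest rates of continuing pregnancies typically included women earlier in gestation". The documents do not support that:
- With a cut at 55/56 days and no gestational-age gradient, simulated power of an exact stratified test is about 0.72. Fisher gives 0.685 at 20/20, but already 0.718 at 21/19 and 0.721 at 22/18, so the apparent gain largely vanishes with an imbalance of one or two women.
- Even with a 15.5-point gradient assumed in both arms, the stratified test reaches only 0.740 at 20/20, below unstratified Boschloo at 0.776.
- A placebo-arm gradient is not established. The weekly table in Section 3 is an uncontrolled treated series pooling several routes, and its authors' figure for untreated women is a flat 25%. The review's 600 mg rows differ by 15 points between 42-day and 49-day limits in one report and by 2 points in another pair.
- The cut is arbitrary, since the weekly table has several boundaries inside 44-63 days.

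In question 2, gestational age is one example beside parity.

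**Conclusion.** The point holds as two limited improvements to a valid plan. Fisher's exact power at 68% v 25% is 0.685 at 20/20 and 0.70-0.72 at splits from 22/18 to 18/22. Boschloo's test adds about 6 to 9 points at each of these splits with size below 5%. It nearly restores the planned 80% but does not guarantee it (0.776 at 20/20). These figures assume two-sided testing, the plan's own rates, and an outcome for every woman.

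The hormone endpoint lacks a suitable method. Baseline adjustment of a continuous log value is at least as precise as a change score under equal variances and clearly better than categorising; the size of the gain depends on an unknown correlation.

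It should not be inferred that the Fisher result would be invalid, or that leaving gestational age out undermines the primary comparison. By-band reporting is missing detail, useful but imprecise.

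**What to change.** Fix the following before unblinding.

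1. **Primary endpoint.** Name an unstratified two-sided Boschloo exact test, ordered by Fisher's p-value, as the single primary test, with Fisher as sensitivity analysis. Record a dated justification, because enrolment was planned to start in February 2019 (Section 5). If Fisher stays primary, restate its power as about 0.69-0.72 at 68% v 25%.
2. **hCG and progesterone.** Add them to the listed evaluations. Analyse log values as continuous outcomes adjusted for the enrollment value, and state for each visit who contributes, given exits after loss of cardiac activity or expulsion.
3. **Optional, descriptive only.** Report continuing pregnancies over women randomized, by arm, within gestational-age bands fixed before unblinding and not chosen from accruing outcomes, with exact CIs, as a rough input to question 3.

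The cost is a few lines of text, a small amount of analysis work and a documented change of primary test. No new data, visits or change to randomization are needed.
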